APPENDIX 9 ECG NORMAL RANGES

Normal Ranges

Age Group 1 to <2 years

Interval	Normal	Abnormal ECG, Clinically Insignificant	Abnormal ECG, Potentially Clinically Significant
HR	Male: 97 – 155 bpm Female: 95 – 178 bpm	Up to the pediatric cardiologist's discretion	Up to the pediatric cardiologist's discretion
PR	Male: 86 – 151 ms Female: 78 – 147 ms	Up to the pediatric cardiologist's discretion	Up to the pediatric cardiologist's discretion
QRS	Male: 54 – 88 ms with no QRS disturbance Female: 54 – 85 ms with no QRS disturbance	Up to the pediatric cardiologist's discretion	Up to the pediatric cardiologist's discretion
QTcF	Male: 383 – 455 ms Female: 381 – 447 ms	Up to the pediatric cardiologist's discretion	Up to the pediatric cardiologist's discretion

Age Group 2 to < 6 years

Interval	Normal	Abnormal ECG, Clinically Insignificant	Abnormal ECG, Potentially Clinically Significant
HR	80-140 bpm	60-79 bpm, or 141-180 bpm	< 60 bpm or > 180 bpm
PR	90-150 ms	Short if <90 ms, otherwise first degree AV block if 151-170 ms	> 170 ms
QRS	≤ 90 ms with no QRS disturbance	91-100 ms with no QRS disturbance or IVCD or any QRS disturbance (except Left Posterior Fascicular Block) with a QRS < 100 ms	IVCD or any QRS conduction disturbance with a QRS > 100 ms
QTcF	Males and Females: 320-450 ms	451-480 ms Increase of QTcF (30 - 60 ms)*	QTcF > 480 ms Short QTcF < 320 ms Increase of QTcF (> 60 ms)*

Note: Baseline, Visit 1 (0) will serve as the baseline for assessment of QTcF increase.

Age Group 6 to < 12 years

Interval	Normal	Abnormal ECG, Clinically Insignificant	Abnormal ECG, Potentially Clinically Significant
HR	60-120 bpm	50-59 bpm, or 121-150 bpm	< 50 bpm or > 150 bpm
PR	100-170 ms	Short if <100 ms, otherwise first degree AV block if 171-190 ms	> 190 ms
QRS	≤ 100 ms with no QRS disturbance	101-110 ms with no QRS disturbance or IVCD or any QRS disturbance (except Left Posterior Fascicular Block) with QRS < 110 ms	IVCD or any QRS conduction disturbance with a QRS > 110 ms
QTcF	Males and Females: 320-450 ms	451-480 ms Increase of QTcF (30 - 60 ms)*	QTcF > 480 ms Short QTcF < 320 ms Increase of QTcF (> 60 ms)*

Note: Baseline, Visit 1 (0) will serve as the baseline for assessment of QTcF increase.

Age Group 12 years and up

Interval	Normal	Abnormal ECG, Clinically Insignificant	Abnormal ECG, Potentially Clinically Significant
HR	50-100 bpm	40-49 bpm, or 101-150 bpm	< 40 bpm or > 150 bpm
PR	110-180 ms	Short if <110 ms, otherwise first degree AV block if 181-220 ms	> 220 ms
QRS	≤ 110 ms with no QRS disturbance	111-120 ms with no QRS disturbance or IVCD or any QRS disturbance (except Left Posterior Fascicular Block) with a QRS < 120 ms	IVCD or any QRS conduction disturbance with a QRS > 120 ms
QTcF	Male: 320-450 ms Female: 320-470 ms	451-500 ms 471-500 ms All ages: Increase of QTcF (30 - 60 ms)*	QTcF > 500 ms QTcF > 500 ms All ages (male/female): Short QTcF < 320 ms All ages: Increase of QTcF (> 60 ms)*

Note: Baseline, Visit 1 (0) will serve as the baseline for assessment of QTcF increase.

APPENDIX 10 EVENTS TO MONITOR

Injection site reactions: based on HLT “Injection site reaction”

Category	PT
Injection site reaction	Embolia cutis medicamentosa
Injection site reaction	Injected limb mobility decreased
Injection site reaction	Injection site abscess
Injection site reaction	Injection site abscess sterile
Injection site reaction	Injection site anaesthesia
Injection site reaction	Injection site atrophy
Injection site reaction	Injection site bruising
Injection site reaction	Injection site calcification
Injection site reaction	Injection site cellulitis
Injection site reaction	Injection site coldness
Injection site reaction	Injection site cyst
Injection site reaction	Injection site dermatitis
Injection site reaction	Injection site discharge
Injection site reaction	Injection site discolouration
Injection site reaction	Injection site discomfort
Injection site reaction	Injection site dryness
Injection site reaction	Injection site dysaesthesia
Injection site reaction	Injection site eczema
Injection site reaction	Injection site erosion
Injection site reaction	Injection site erythema
Injection site reaction	Injection site exfoliation
Injection site reaction	Injection site extravasation
Injection site reaction	Injection site fibrosis
Injection site reaction	Injection site granuloma
Injection site reaction	Injection site haematoma
Injection site reaction	Injection site haemorrhage
Injection site reaction	Injection site hyperaesthesia
Injection site reaction	Injection site hypersensitivity
Injection site reaction	Injection site hypertrichosis
Injection site reaction	Injection site hypertrophy
Injection site reaction	Injection site hypoaesthesia
Injection site reaction	Injection site induration
Injection site reaction	Injection site infection
Injection site reaction	Injection site inflammation
Injection site reaction	Injection site injury
Injection site reaction	Injection site irritation
Injection site reaction	Injection site ischaemia
Injection site reaction	Injection site joint discomfort

Category	PT
Injection site reaction	Injection site joint effusion
Injection site reaction	Injection site joint erythema
Injection site reaction	Injection site joint infection
Injection site reaction	Injection site joint inflammation
Injection site reaction	Injection site joint movement impairment
Injection site reaction	Injection site joint pain
Injection site reaction	Injection site joint swelling
Injection site reaction	Injection site joint warmth
Injection site reaction	Injection site laceration
Injection site reaction	Injection site lymphadenopathy
Injection site reaction	Injection site macule
Injection site reaction	Injection site mass
Injection site reaction	Injection site movement impairment
Injection site reaction	Injection site necrosis
Injection site reaction	Injection site nerve damage
Injection site reaction	Injection site nodule
Injection site reaction	Injection site oedema
Injection site reaction	Injection site pain
Injection site reaction	Injection site pallor
Injection site reaction	Injection site papule
Injection site reaction	Injection site paraesthesia
Injection site reaction	Injection site phlebitis
Injection site reaction	Injection site photosensitivity reaction
Injection site reaction	Injection site plaque
Injection site reaction	Injection site pruritus
Injection site reaction	Injection site pustule
Injection site reaction	Injection site rash
Injection site reaction	Injection site reaction
Injection site reaction	Injection site recall reaction
Injection site reaction	Injection site scab
Injection site reaction	Injection site scar
Injection site reaction	Injection site streaking
Injection site reaction	Injection site swelling
Injection site reaction	Injection site thrombosis
Injection site reaction	Injection site ulcer
Injection site reaction	Injection site urticaria
Injection site reaction	Injection site vasculitis
Injection site reaction	Injection site vesicles
Injection site reaction	Injection site warmth
Injection site reaction	Malabsorption from injection site

Hypersensitivity: based on relevant PTs in the narrow SMQs for “Hypersensitivity”,

Category	PT
Hypersensitivity	Acute generalised exanthematous pustulosis
Hypersensitivity	Administration site dermatitis
Hypersensitivity	Administration site eczema
Hypersensitivity	Administration site hypersensitivity
Hypersensitivity	Administration site rash
Hypersensitivity	Administration site recall reaction
Hypersensitivity	Administration site urticaria
Hypersensitivity	Administration site vasculitis
Hypersensitivity	Allergic bronchitis
Hypersensitivity	Allergic colitis
Hypersensitivity	Allergic cough
Hypersensitivity	Allergic cystitis
Hypersensitivity	Allergic eosinophilia
Hypersensitivity	Allergic gastroenteritis
Hypersensitivity	Allergic granulomatous angiitis
Hypersensitivity	Allergic hepatitis
Hypersensitivity	Allergic keratitis
Hypersensitivity	Allergic myocarditis
Hypersensitivity	Allergic oedema
Hypersensitivity	Allergic otitis externa
Hypersensitivity	Allergic otitis media
Hypersensitivity	Allergic pharyngitis
Hypersensitivity	Allergic respiratory disease
Hypersensitivity	Allergic respiratory symptom
Hypersensitivity	Allergic sinusitis
Hypersensitivity	Allergic transfusion reaction
Hypersensitivity	Allergy alert test positive
Hypersensitivity	Allergy test positive
Hypersensitivity	Allergy to immunoglobulin therapy
Hypersensitivity	Allergy to vaccine
Hypersensitivity	Alveolitis allergic
Hypersensitivity	Anaphylactic reaction
Hypersensitivity	Anaphylactic shock
Hypersensitivity	Anaphylactic transfusion reaction
Hypersensitivity	Anaphylactoid reaction
Hypersensitivity	Anaphylactoid shock
Hypersensitivity	Anaphylaxis treatment
Hypersensitivity	Angioedema
Hypersensitivity	Antiallergic therapy
Hypersensitivity	Antiendomysial antibody positive
Hypersensitivity	Anti-neutrophil cytoplasmic antibody positive vasculitis
Hypersensitivity	Application site dermatitis
Hypersensitivity	Application site eczema
Hypersensitivity	Application site hypersensitivity

Category	PT
Hypersensitivity	Application site rash
Hypersensitivity	Application site recall reaction
Hypersensitivity	Application site urticaria
Hypersensitivity	Application site vasculitis
Hypersensitivity	Arthritis allergic
Hypersensitivity	Atopy
Hypersensitivity	Blepharitis allergic
Hypersensitivity	Blood immunoglobulin E abnormal
Hypersensitivity	Blood immunoglobulin E increased
Hypersensitivity	Bromoderma
Hypersensitivity	Bronchospasm
Hypersensitivity	Catheter site dermatitis
Hypersensitivity	Catheter site eczema
Hypersensitivity	Catheter site hypersensitivity
Hypersensitivity	Catheter site rash
Hypersensitivity	Catheter site urticaria
Hypersensitivity	Catheter site vasculitis
Hypersensitivity	Chronic eosinophilic rhinosinusitis
Hypersensitivity	Chronic hyperplastic eosinophilic sinusitis
Hypersensitivity	Circulatory collapse
Hypersensitivity	Circumoral oedema
Hypersensitivity	Conjunctival oedema
Hypersensitivity	Conjunctivitis allergic
Hypersensitivity	Corneal oedema
Hypersensitivity	Cutaneous vasculitis
Hypersensitivity	Dennie-Morgan fold
Hypersensitivity	Dermatitis
Hypersensitivity	Dermatitis acneiform
Hypersensitivity	Dermatitis allergic
Hypersensitivity	Dermatitis atopic
Hypersensitivity	Dermatitis bullous
Hypersensitivity	Dermatitis contact
Hypersensitivity	Dermatitis exfoliative
Hypersensitivity	Dermatitis exfoliative generalised
Hypersensitivity	Dermatitis herpetiformis
Hypersensitivity	Dermatitis infected
Hypersensitivity	Dermatitis psoriasiform
Hypersensitivity	Distributive shock
Hypersensitivity	Documented hypersensitivity to administered product
Hypersensitivity	Drug cross-reactivity
Hypersensitivity	Drug eruption
Hypersensitivity	Drug hypersensitivity
Hypersensitivity	Drug provocation test
Hypersensitivity	Drug reaction with eosinophilia and systemic symptoms
Hypersensitivity	Eczema
Hypersensitivity	Eczema infantile

Category	PT
Hypersensitivity	Eczema nummular
Hypersensitivity	Eczema vaccinatum
Hypersensitivity	Eczema vesicular
Hypersensitivity	Eczema weeping
Hypersensitivity	Encephalitis allergic
Hypersensitivity	Encephalopathy allergic
Hypersensitivity	Epidermal necrosis
Hypersensitivity	Epidermolysis
Hypersensitivity	Epidermolysis bullosa
Hypersensitivity	Epiglottic oedema
Hypersensitivity	Erythema multiforme
Hypersensitivity	Erythema nodosum
Hypersensitivity	Exfoliative rash
Hypersensitivity	Eye allergy
Hypersensitivity	Eye oedema
Hypersensitivity	Eye swelling
Hypersensitivity	Eyelid oedema
Hypersensitivity	Face oedema
Hypersensitivity	Giant papillary conjunctivitis
Hypersensitivity	Gingival oedema
Hypersensitivity	Gingival swelling
Hypersensitivity	Gleich's syndrome
Hypersensitivity	Haemorrhagic urticaria
Hypersensitivity	Hand dermatitis
Hypersensitivity	Henoch-Schonlein purpura
Hypersensitivity	Henoch-Schonlein purpura nephritis
Hypersensitivity	Hereditary angioedema
Hypersensitivity	Hypersensitivity
Hypersensitivity	Hypersensitivity vasculitis
Hypersensitivity	Idiopathic urticaria
Hypersensitivity	Immediate post-injection reaction
Hypersensitivity	Immune thrombocytopenic purpura
Hypersensitivity	Immune tolerance induction
Hypersensitivity	Infusion site dermatitis
Hypersensitivity	Infusion site eczema
Hypersensitivity	Infusion site hypersensitivity
Hypersensitivity	Infusion site rash
Hypersensitivity	Infusion site recall reaction
Hypersensitivity	Infusion site urticaria
Hypersensitivity	Infusion site vasculitis
Hypersensitivity	Injection site dermatitis
Hypersensitivity	Injection site eczema
Hypersensitivity	Injection site hypersensitivity
Hypersensitivity	Injection site rash
Hypersensitivity	Injection site recall reaction
Hypersensitivity	Injection site urticaria

Category	PT
Hypersensitivity	Injection site vasculitis
Hypersensitivity	Instillation site hypersensitivity
Hypersensitivity	Instillation site rash
Hypersensitivity	Instillation site urticaria
Hypersensitivity	Interstitial granulomatous dermatitis
Hypersensitivity	Intestinal angioedema
Hypersensitivity	Iodine allergy
Hypersensitivity	Kaposi's varicelliform eruption
Hypersensitivity	Kounis syndrome
Hypersensitivity	Laryngeal oedema
Hypersensitivity	Laryngitis allergic
Hypersensitivity	Laryngospasm
Hypersensitivity	Laryngotracheal oedema
Hypersensitivity	Limbal swelling
Hypersensitivity	Lip oedema
Hypersensitivity	Lip swelling
Hypersensitivity	Mast cell degranulation present
Hypersensitivity	Mouth swelling
Hypersensitivity	Mucocutaneous rash
Hypersensitivity	Multiple allergies
Hypersensitivity	Nephritis allergic
Hypersensitivity	Nikolsky's sign
Hypersensitivity	Nodular rash
Hypersensitivity	Oculomucocutaneous syndrome
Hypersensitivity	Oculo-respiratory syndrome
Hypersensitivity	Oedema mouth
Hypersensitivity	Oral allergy syndrome
Hypersensitivity	Oropharyngeal blistering
Hypersensitivity	Oropharyngeal spasm
Hypersensitivity	Oropharyngeal swelling
Hypersensitivity	Palatal oedema
Hypersensitivity	Palatal swelling
Hypersensitivity	Palisaded neutrophilic granulomatous dermatitis
Hypersensitivity	Palpable purpura
Hypersensitivity	Pathergy reaction
Hypersensitivity	Periorbital oedema
Hypersensitivity	Pharyngeal oedema
Hypersensitivity	Pruritus allergic
Hypersensitivity	Radioallergosorbent test positive
Hypersensitivity	Rash
Hypersensitivity	Rash erythematous
Hypersensitivity	Rash follicular
Hypersensitivity	Rash generalised
Hypersensitivity	Rash macular
Hypersensitivity	Rash maculo-papular
Hypersensitivity	Rash maculovesicular

Category	PT
Hypersensitivity	Rash morbilliform
Hypersensitivity	Rash neonatal
Hypersensitivity	Rash papulosquamous
Hypersensitivity	Rash pruritic
Hypersensitivity	Rash pustular
Hypersensitivity	Rash rubelliform
Hypersensitivity	Rash scarlatiniform
Hypersensitivity	Rash vesicular
Hypersensitivity	Reaction to azo-dyes
Hypersensitivity	Reaction to colouring
Hypersensitivity	Reaction to drug excipients
Hypersensitivity	Reaction to preservatives
Hypersensitivity	Red man syndrome
Hypersensitivity	Rhinitis allergic
Hypersensitivity	Scleral oedema
Hypersensitivity	Scleritis allergic
Hypersensitivity	Scrotal oedema
Hypersensitivity	Serum sickness
Hypersensitivity	Serum sickness-like reaction
Hypersensitivity	Shock
Hypersensitivity	Shock symptom
Hypersensitivity	Skin necrosis
Hypersensitivity	Skin reaction
Hypersensitivity	Skin test positive
Hypersensitivity	Solar urticaria
Hypersensitivity	Solvent sensitivity
Hypersensitivity	Stevens-Johnson syndrome
Hypersensitivity	Stoma site hypersensitivity
Hypersensitivity	Stoma site rash
Hypersensitivity	Swelling face
Hypersensitivity	Swollen tongue
Hypersensitivity	Tongue oedema
Hypersensitivity	Toxic epidermal necrolysis
Hypersensitivity	Toxic skin eruption
Hypersensitivity	Tracheal oedema
Hypersensitivity	Type I hypersensitivity
Hypersensitivity	Type II hypersensitivity
Hypersensitivity	Type III immune complex mediated reaction
Hypersensitivity	Type IV hypersensitivity reaction
Hypersensitivity	Urticaria
Hypersensitivity	Urticaria cholinergic
Hypersensitivity	Urticaria chronic
Hypersensitivity	Urticaria contact
Hypersensitivity	Urticaria papular
Hypersensitivity	Urticaria physical
Hypersensitivity	Urticaria pigmentosa

Category	PT
Hypersensitivity	Urticaria vesiculosa
Hypersensitivity	Vaginal exfoliation
Hypersensitivity	Vaginal ulceration
Hypersensitivity	Vasculitic rash
Hypersensitivity	Vessel puncture site rash
Hypersensitivity	Vulval ulceration
Hypersensitivity	Vulvovaginal rash
Hypersensitivity	Vulvovaginal ulceration

Hyperphosphataemia: based on selected PTs below

Category	PT
Hyperphosphataemia	Hyperphosphataemia
Hyperphosphataemia	Blood phosphorus increased

Ectopic mineralization: based on a MedDRA search of ‘calcification’

Category	PT
Ectopic calcification	Adrenal calcification
Ectopic calcification	Aortic calcification
Ectopic calcification	Aortic valve calcification
Ectopic calcification	Aortic valve sclerosis
Ectopic calcification	Articular calcification
Ectopic calcification	Bladder wall calcification
Ectopic calcification	Breast calcifications
Ectopic calcification	Bursa calcification
Ectopic calcification	Calcific deposits removal
Ectopic calcification	Calcification metastatic
Ectopic calcification	Calcification of muscle
Ectopic calcification	Calcinosis
Ectopic calcification	Calculus bladder
Ectopic calcification	Calculus prostatic
Ectopic calcification	Calculus ureteric
Ectopic calcification	Calculus urethral
Ectopic calcification	Calculus urinary
Ectopic calcification	Cardiac valve sclerosis
Ectopic calcification	Cerebral calcification
Ectopic calcification	Chondrocalcinosis
Ectopic calcification	Chondrocalcinosis pyrophosphate
Ectopic calcification	Cutaneous calcification
Ectopic calcification	Dystrophic calcification
Ectopic calcification	Heart valve calcification

Category	PT
Ectopic calcification	Heart valve stenosis
Ectopic calcification	Hepatic calcification
Ectopic calcification	Intervertebral disc calcification
Ectopic calcification	Intestinal calcification
Ectopic calcification	Ligament calcification
Ectopic calcification	Lymph node calcification
Ectopic calcification	Mitral valve calcification
Ectopic calcification	Mitral valve sclerosis
Ectopic calcification	Myocardial calcification
Ectopic calcification	Nephrocalcinosis
Ectopic calcification	Nephrolithiasis
Ectopic calcification	Ovarian calcification
Ectopic calcification	Pancreatic calcification
Ectopic calcification	Pericardial calcification
Ectopic calcification	Pleural calcification
Ectopic calcification	Prostatic calcification
Ectopic calcification	Pulmonary calcification
Ectopic calcification	Pulmonary valve calcification
Ectopic calcification	Pulmonary valve sclerosis
Ectopic calcification	Splenic calcification
Ectopic calcification	Stag horn calculus
Ectopic calcification	Tendon calcification
Ectopic calcification	Tracheal calcification
Ectopic calcification	Tricuspid valve calcification
Ectopic calcification	Tricuspid valve sclerosis
Ectopic calcification	Vascular calcification

Restless legs syndrome

Category	PT
Restless legs syndrome	Restless legs syndrome
Restless legs syndrome	Restlessness
Restless legs syndrome	Akathisia
Restless legs syndrome	Psychomotor hyperactivity
Restless legs syndrome	Sensory disturbance
Restless legs syndrome	Muscle cramp
Restless legs syndrome	Limb discomfort
Restless legs syndrome	Neuromuscular pain
Restless legs syndrome	Formication

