to Week 40 by 30% ($p=0.0076$) as assessed by the Thatcher Rickets Severity Score (RSS), with greater improvements seen with Q2W dosing (44% reduction; $p=0.0126$) than with Q4W dosing (14% reduction). The greatest improvement was observed in a subset of patients ($n=18$) with clear evidence of rickets at baseline (baseline RSS ≥ 1.5) (59% reduction with Q2W dosing and 47% reduction with Q4W dosing; $p<0.0001$ for both dose groups). Consistency in the rickets results was observed using the Radiographic Global Impression of Change (RGI-C; -3=worsening; +3=complete healing), with rickets improving by +1.56 points ($p<0.0001$) in the Q2W dosing group and by +1.20 points ($p<0.0001$) in the Q4W dosing group at Week 40. In the subgroup with a baseline RSS ≥ 1.5 , RGI-C improved by +2.0 points ($p<0.0001$) in patients who received Q2W dosing, indicating substantial healing of rickets, and by +1.70 ($p<0.0001$) in patients who received Q4W dosing. The 40-week analysis also revealed that the Q4W dosing group showed a peak in serum phosphorus at 2 weeks after dosing followed by a decrease in serum phosphorus levels before the next dose (though remaining above baseline), whereas the Q2W regimen showed stable serum phosphorus levels slowly increasing over time. Overall, the dose-response and PD results observed in the pediatric study were consistent with the adult XLH data generated to date. None of the subjects had serum phosphorus levels above the normal range in either dosing group. Most treatment-related adverse events (AE) were mild, most commonly a transient injection site reaction (39%). One child experienced a serious AE and was hospitalized for fever/muscle pain that improved and continues in the trial. No clinically meaningful changes occurred in serum or urine calcium, serum iPTH, or renal ultrasound.

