5.15 Adverse Events to Monitor

The definition for each type of adverse events to monitor is as the following:

- Injection Site Reaction is defined by preferred terms under the Medical Dictionary for Regulatory Activities (MedDRA) high-level term (HLT) “Injection site reaction”
- Hypersensitivity AE: Defined using relevant PTs in the narrow SMQs for “Hypersensitivity”.
- Hyperphosphataemia AE: Defined by using PTs: “Hyperphosphataemia”, “Blood phosphorus increased”, “Blood phosphorus abnormal”.
- Ectopic calcification related AE: There is no available SMQ. Ectopic calcification related AE is defined using a MedDRA search of ‘calcification’.
- Restless leg syndrome AE: Defined by PTs “Restless legs syndrome”, “Restlessness”, “Akathisia”, “Sensory disturbance”, “Psychomotor hyperactivity”, “Limb discomfort”, “Neuromuscular pain”, “Formication”.

See [Appendix 10](#) for the search criteria.

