8.8.1 Adverse Events

Adverse events will be coded by system organ class and preferred term using the Medical Dictionary for Regulatory Activities.

An AE (classified by preferred term) will be considered a treatment emergent adverse event (TEAE) if it occurred on or after the first dose of investigational product and was not present prior to the first dose, or it was present before the first dose but increased in severity during the study.

Subject incidence of TEAEs will be tabulated as the following:

- Summary of TEAEs by treatment group
- TEAEs by SOC and PT (preferred term) by treatment group (sorted by descending frequency by SOC and PT)

- Related TEAEs by SOC and PT by treatment group (sorted by descending frequency by SOC and PT) or TEAE by greatest relationship, SOC and PT by treatment group
- Serious TEAEs by SOC and PT by treatment group (sorted by descending frequency by SOC and PT).
- Serious and Related TEAEs by SOC and PT by treatment group (sorted by descending frequency by SOC and PT).
- Grade 3 or 4 TEAEs by SOC and PT by treatment group (sorted by descending frequency by SOC and PT). or TEAE by greatest severity, treatment group, SOC and PT
- Deaths by SOC and PT by treatment group (sorted by descending frequency by SOC and PT).
- TEAEs leading to discontinuation of study by SOC and PT by treatment group (sorted by descending frequency by SOC and PT).
- TEAEs leading to discontinuation of treatment by SOC and PT by treatment group (sorted by descending frequency by SOC and PT).
- TEAEs by PT by treatment group (sorted by descending frequency of PT)
- Serious TEAEs by PT by treatment group (sorted by descending frequency of PT)
- Related TEAEs by PT by treatment group (sorted by descending frequency of PT)

Subject incidence for each type of events to monitor will be tabulated as the following:

- By PT by treatment group
- By PT and greatest reported severity by treatment group
- By PT and relationship to study drug by treatment group

Detailed listings for all AEs, serious TEAEs, AEs leading to the discontinuation of study, AEs leading to the discontinuation of treatment, and death will also be generated.

The severity will be based on Common Terminology Criteria for Adverse Events (CTCAE), Version 4.0. If an AE cannot be graded based on CTCAE, the investigator will assign a severity based on 1 = mild, 2 = moderate, 3 = severe, 4 = life threatening, and 5 = Death.

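### Seven injection-site terms count as hypersensitivity as well as injection site reaction, so the by-arm hypersensitivity incidence mixes a difference in route of administration with non-local hypersensitivity

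*SAP*

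**What the plan says.** SAP 5.15 defines the events to monitor. Injection Site Reaction is every PT under the MedDRA high-level term of that name. The other group is introduced as "Hypersensitivity AE: Defined using relevant PTs in the narrow SMQs for" hypersensitivity. Appendix 10 then writes out both lists.

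Seven PTs stand in both lists: "Injection site dermatitis", "Injection site hypersensitivity" and "Injection site urticaria", and the injection-site terms for eczema, rash, recall reaction and vasculitis. No rule assigns a shared term to one group, and no hypersensitivity summary leaves the local terms out.

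SAP 8.8.1 states: "Subject incidence for each type of events to monitor will be tabulated as the following". Three tabulations follow, each by treatment group: by PT, by PT and greatest severity, and by PT and relationship. SAP 8.8 makes the safety summaries descriptive. The safety objective in SAP 2.4 is comparative, KRN23 against active control.

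**The concern.** A KRN23 child whose only event is a rash at the needle site is counted under hypersensitivity. A control child takes oral phosphate and active vitamin D, and that treatment cannot produce the same event. The two arms can therefore differ in hypersensitivity incidence even when non-local hypersensitivity is equally common in both.

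Hypersensitivity to a monoclonal antibody is one of the few events that the SAP singles out for monitoring. With about 30 children per arm, a few local reactions can change how that line reads. They may suggest a systemic signal that is not there. They may also lead a reader to dismiss a real non-local excess as merely injection-site events.

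**Working it through.** **1. Overlap of the lists.** The Injection site reaction list in Appendix 10 has 78 PTs. The Hypersensitivity list has seven PTs beginning 'Injection site', and all seven are among the 78. The overlap is exactly seven.

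**2. Neighbouring terms.** 'Immediate post-injection reaction' is in the Hypersensitivity list only. So are seven 'Administration site' PTs (dermatitis, eczema, hypersensitivity, rash, recall reaction, urticaria, vasculitis), to which a needle-site event could also be coded. The PT 'Injection site reaction' itself is in the Injection site reaction list only.

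**3. Route.** KRN23 is given subcutaneously (SAP 3.3) and the control is oral (SAP 3.2). Protocol 7.5.1 adds that control children need no health professional to give their medicine.

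**4. What the PT rows can show.** One child may have several PTs. Subtracting the seven local rows from the group total removes a child with two local terms twice, and also removes a child who has both a local and a non-local term. The number of children with at least one non-local term therefore cannot in general be recovered from PT counts. It can be recovered from the subject-level listings that SAP 8.8.1 also requires.

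**5. Size, as an illustration.** The plan gives no figure to reproduce. The inputs are:

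- 0.39, the Phase 2 paediatric injection site reaction frequency in Protocol 5.2.3, assumed to carry over to KRN23 children here
- s, the share of those children coded to at least one of the seven PTs (assumed, 0 to 50%)
- b, the non-local hypersensitivity rate, equal in both arms (assumed, 10 to 30%)
- independence of local and non-local events (assumed)
- 30 children per arm (SAP 3.5)

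KRN23 incidence = 1 − (1 − b)(1 − 0.39s), and control incidence = b. The added excess is (1 − b) × 0.39s.

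| s | b = 10% | b = 20% | b = 30% |
|---|---|---|---|
| 0% | 0 | 0 | 0 |
| 10% | 3.5 points | 3.1 | 2.7 |
| 25% | 8.8 | 7.8 | 6.8 |
| 50% | 17.6 | 15.6 | 13.7 |

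For s = 10% and b = 10%: 1 − 0.90 × 0.961 = 13.5% in KRN23 against 10% in control. For s = 50% and b = 10%: 1 − 0.90 × 0.805 = 27.6% against 10%. In children, the largest excess is 0.1755 × 30 = 5.3. At s = 10% it is 0.0273 × 30 = 0.8 to 0.0351 × 30 = 1.1.

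**6. After the change.** Without the seven PTs the overlap is zero, and under the same assumptions both arms read b.

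**The case against.** The best defence is that the definition is deliberate. The group is built from a stated standard search, the narrow SMQ, and as listed that search contains these terms. Including too much is the cautious direction when monitoring an antibody, and a reaction at the needle site can be immunological. This stands. A reader might infer that Appendix 10 contains a copying error; nothing in the documents supports that, and the full group should stay.

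Second, the summaries are descriptive, each local term has its own row by arm, and all adverse events are listed. This also stands, in part. The information is not lost, but a reader of the tables alone cannot obtain the subject count. The three tabulations in SAP 8.8.1 do not name a group-total row either; that one is meant is inferred from the sentence introducing them.

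Third, the size may be small or nil. Protocol 5.2.3 does not say whether its 39% is the PT 'Injection site reaction' or the whole group. If it is the PT, it says nothing about the seven terms. The adult data in the same section name injection site reaction (22.7%) and injection site pain (9.1%), neither of which is among the seven, though that list may be incomplete. No document gives the coding share; seven of 78 listed terms is 9%, which is no estimate of it. This objection stands, and it is why the range starts at zero.

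Fourth, control children can receive injections outside the study. A reader might infer that they cannot have these events at all. The documents support only that study treatment cannot cause the events in that arm during the Treatment Period.

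**Conclusion.** The concern holds as a comparability problem. Seven PTs count in two groups, study treatment can cause them in one arm only during the 64 weeks, and the SAP has no subject-level hypersensitivity count without them. The seven terms can only add to the incidence in the arm that is injected.

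The added KRN23 excess is 0 to about 18 percentage points (0 to about 5 of 30 children), and about 3 points (one child) at a 10% coding share. That range rests on carrying over the 39%, on the assumed coding share, on an equal 10 to 30% non-local rate and on independence.

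A reader might infer that a material false signal is likely. The documents do not support this: the coding share has no source, the SAP sets no threshold for a signal, and no safety test is planned. No efficacy analysis is affected. The change is a cheap improvement to how a descriptive table can be read.

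**What to change.** Keep the narrow-SMQ Hypersensitivity group as defined and reported. In SAP 8.8.1 and Appendix 10:

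- Add a subject-level row by treatment group, 'Hypersensitivity excluding injection-site PTs', that drops the seven shared terms. Show it beside a subject-level row for the full group, so that both are read in the KRN23-versus-control comparison.
- Keep 'Immediate post-injection reaction' in the new row, because no other group holds it.
- Apply the same exclusion to any 'Administration site' PT that records a KRN23 needle-site event. Such an event stays visible in the full row. The PT alone does not identify it, so the case has to be checked.
- State that one event may count in two groups.

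The cost is SAP wording, one more row per table and a case check for any 'Administration site' events. Data collection, design and patient care do not change. The downside is that the added row is not the unmodified SMQ, which is why the two rows should always appear together.
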